### *Secondary*

2.2 To determine the time to progression (TTP) and overall survival (OS) in this patient population

2.3 To evaluate the impact of SBRT on the QOL of subjects in the adjuvant setting

2.5 To evaluate the acute and late toxicities associated with SBRT for pancreas cancer

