### 6.2 Evaluation during treatment

The subjects will be carefully followed while on active treatment and post-treatment for 24 months, or until death. Evaluation during treatment will consist of the following activities:

- 6.2.1 Administration of SBRT
- 6.2.3 Interim medical history and physical examination at baseline, prior to SBRT treatment, at the end of SBRT, and 10-12 weeks after SBRT then every 3 months thereafter for up to 24 months.
- 6.2.4 Serum chemistry and electrolytes to include BUN, creatinine, sodium, potassium, bicarbonate, chloride, calcium, magnesium, glucose, total bilirubin, AST, ALT, alkaline phosphatase post-treatment as clinically indicated
- 6.2.5 Hematologic studies to include CBC with differential and platelet count prior to SBRT and repeated 10-12 weeks later and then at follow-up as clinically indicated.
- 6.2.6 CT scan will be obtained at 10-12 weeks post-treatment and will be reviewed for evidence of response. Since these subjects will likely have no gross disease on imaging, the main goal of the follow-up scans is to monitor for local and distant progression as defined below.

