#### *6.4.4 QOL evaluation*

QOL evaluation will be carried out according to the treatment schema in section 6.0. The survey will be the FACT-G and will be administered prior to SBRT, after completion of SBRT, and at each follow-up. See appendix A for more details.

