#### 7.3.3 Analysis of Study Endpoints

Survival (LPFS, OS, TTP) will be estimated by the Kaplan-Meier method for all evaluable patients and the corresponding median survival times (with 95% confidence interval) reported. The 2-year LPFS will also be estimated along with its 95% confidence interval. The effect of variables listed in Section 7.3.2 will be explored with Cox regression models.

For the QOL data analysis, each item of the FACT-G will be individually assessed. The mean and standard deviation of the observed data will be summarized at each collection time and plotted against time, from baseline through the end of patient follow-up. Generalized linear models (such as cumulative logit models) for repeated measures will be used to explore if there are significant changes in HRQOL over time.

Using NCI Common Terminology Criteria for Adverse Events (CTCAE v4.0), the number of patients experiencing adverse events over their course of treatment will be characterized by type of adverse event and grade, by the time of onset in relation to the first day of therapy, and whether the event is clinically significant. Attribution of adverse events to treatment (unrelated, unlikely, possibly, probably, or definitely) will also be summarized for any serious adverse events (SAEs), CTCAE grade 3 or higher. The percentage of patients experiencing SAEs that are considered to be treatment-related (probable or definite) will be determined. The percentage of patients experiencing the acute and late toxicities associated with SBRT (as defined in Section 6.4) will also be estimated along with its 95% confidence interval.

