#### 8.1.1 Subject Removal Criteria

1. Disease progression
2. Development of a serious medical illness
3. Evidence of dose-limiting toxicity
4. Voluntary withdrawal
5. Protocol violation
6. Discretion of the principal investigator
7. Development of grade 4 toxicity related to experimental therapeutic

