**PHYSICAL WELL-BEING**

		Not at all	A little bit	Some-what	Quite a bit	Very much
GP1	I have a lack of energy.....	0	1	2	3	4
GP2	I have nausea .....	0	1	2	3	4
GP3	Because of my physical condition, I have trouble meeting the needs of my family .....	0	1	2	3	4
GP4	I have pain .....	0	1	2	3	4
GP5	I am bothered by side effects of treatment .....	0	1	2	3	4
GP6	I feel ill .....	0	1	2	3	4
GP7	I am forced to spend time in bed .....	0	1	2	3	4

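### The planned plot of observed FACT-G item means over 24 months can be biased toward apparent improvement by deaths, and the plan neither shows who remains nor states a missing-data assumption

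*Combined protocol and SAP*

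**What the plan says.** Quality of life is a secondary objective (Section 2.0): "To evaluate the impact of SBRT on the QOL of subjects in the adjuvant setting". Section 6.4.4 says that the FACT-G "will be administered prior to SBRT, after completion of SBRT, and at each follow-up". By the schedule in Section 6.3, follow-up visits fall at 10-12 weeks and then every 3 months to 24 months. Section 6.2 sets the length of follow-up: "The subjects will be carefully followed while on active treatment and post-treatment for 24 months, or until death".

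Section 7.3.3 sets the analysis in three parts:

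- The unit is the single item: "each item of the FACT-G will be individually assessed". No total or subscale score is planned.
- The display is descriptive: "The mean and standard deviation of the observed data will be summarized at each collection time and plotted against time".
- Change is explored with generalized linear models, with cumulative logit models as the example, which "for repeated measures will be used to explore if there are significant changes in HRQOL over time".

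Section 8.1.1 lists "Disease progression" first among the criteria for removing a subject. It does not say whether removal ends FACT-G collection.

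No section says how FACT-G data lost through death, progression or non-completion will be handled, or asks for the numbers alive and responding at each visit.

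**The concern.** A mean of observed data at each visit is a mean over whoever is still there. When many patients die during follow-up, the baseline mean and the 24-month mean belong to different groups. If patients with poorer quality of life tend to die or drop out sooner, the later group was better off from the start. The line joining the means then mixes change within patients with change in who is measured.

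The trial has one arm, so change over time is its only evidence on the quality-of-life objective. A report could state that quality of life was kept or improved after SBRT when part or all of the pattern comes from loss of sicker patients.

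**Working it through.** **The plan's own figure.** There is none for quality of life or for expected overall survival (OS). The power statement concerns local progression-free survival, and this point does not depend on it.

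**Step 1: how many would remain at 24 months.** The inputs are the median OS figures in the background sections on adjuvant radiation and on chemotherapy alone. A median below 24 months already means that more than half died by then. The exponential form, S(24) = 0.5^(24/median), is an assumption used only to attach a percentage.

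| Cited median OS (months) | Source | Dead by 24 months | Alive of 50 |
|---|---|---|---|
| 11 | control arm, small phase III chemoradiation trial | 78% | 11 |
| 14 | no chemotherapy, 2x2 factorial trial | 70% | 15 |
| 19.7 | chemotherapy, same factorial trial | 57% | 21 to 22 |
| 20 | experimental arm, small phase III trial | 56% | 22 |
| 21.2 | chemoradiation, series of over 600 patients | 54% | 23 |
| 22 | adjuvant gemcitabine trial | 53% | 23 to 24 |
| 25.2 | chemoradiation, series of R0 resections only | 48% | 26 |

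The exception, 25.2 months, comes from patients who all had an R0 resection. This trial enrols patients with close or positive margins.

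**Step 2: size of the shift if no patient changes.** Hold each patient's quality of life constant with SD 1. Let it correlate r with survival time on a normal scale (assumption). Among the surviving fraction f, the mean moves by

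shift = r × φ(z)/f, where z is the point with upper-tail area f.

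At a median of 20 months, f = 0.5^(24/20) = 0.435, z = 0.163, φ(z) = 0.394 and φ(z)/f = 0.904. Then:

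- r = 0: shift 0
- r = 0.2: 0.2 × 0.904 = 0.18 SD
- r = 0.3: 0.3 × 0.904 = 0.27 SD
- r = 0.4: 0.4 × 0.904 = 0.36 SD

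The documents give no value for r.

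**Step 3: a second mechanism.** Instead of a correlation, suppose the death hazard is multiplied by 1.35 to 1.65 for each SD of worse quality of life (assumption). Simulated shifts at 24 months are:

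- median OS 20 months: 0.24 to 0.37 SD
- median OS 14 months: 0.33 to 0.50 SD
- median OS 25.2 months: 0.19 to 0.31 SD

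For scale, the standard error of a mean from 22 patients is 1/√22 = 0.21 SD.

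**Step 4: true decline.** At a median of 20 months and a hazard ratio of 1.35, a real decline of 0.01 SD per month gives 0.24 − 24 × 0.01 = 0, so the plot looks flat. A decline of 0.02 SD per month gives 0.24 − 0.48 = −0.24 SD. With a hazard ratio of 1.65 it gives 0.37 − 0.48 = −0.11 SD. The plotted line can therefore rise, stay level or fall. In each case it looks better than the patients' own course.

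**Step 5: direction by item.** Items in Appendix A run from 0 to 4. On GP1-GP7 (for example "I have a lack of energy"), GE1 and GE3-GE6, a higher score is worse. That is 7 + 5 = 12 of 7 + 7 + 6 + 7 = 27 items. On these, loss of sicker patients lowers the raw mean; on the other 15 it raises it. Both directions read as improvement.

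**Step 6: loss at progression.** If FACT-G collection stopped at progression, with the 14-month disease-free survival of the gemcitabine trial taken as the median, then f = 0.5^(24/14) = 0.305, φ(z)/f = 1.149, and the shift at r = 0.3 is about 0.34 SD. This is conditional, because the documents do not say that removal ends collection.

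**The case against.** The strongest reply is that change over time is to be explored with repeated-measures models and not by comparing raw means. Fitted with random effects by likelihood, a cumulative logit model would suit 0-4 items and would be valid when missingness depends on observed quality of life. This stands in part. But Section 7.3.3 does not say whether the model is random-effects or marginal, and a marginal model generally needs missingness unrelated to quality of life. Neither kind defines quality of life after death, and neither corrects the plot.

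A second reply is that if every survivor responds, the observed mean is a correct mean among those alive at that visit. That is true, and it is a legitimate description. The difficulty is reading the joined means as a course over time when the group is shrinking and its size is not shown.

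Three stronger readings are tempting, and the documents do not support them:

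- A reader might infer that the curve must rise. That needs a link between quality of life and survival, for which the documents give no figure. True decline can cancel it, and on 12 items the bias runs downward.
- A reader might infer that the protocol expects more than half of its patients to die within 24 months. It states no expected OS. The share is carried over from cited background series, one of which implies 48%.
- A reader might infer that progression ends assessment. Section 8.1.1 does not say so, and Section 6.2 follows subjects for 24 months or until death.

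It is also fair that the objective is secondary, the models are exploratory, and no decision rule rests on them. The single arm and the discretionary systemic therapy after SBRT (Section 3.5) already limit what can be attributed to SBRT.

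**Conclusion.** The point holds as a risk of bias in a stated display. The observed item means can be biased toward apparent improvement by about 0.2 to 0.4 SD at 24 months. This rests on a median OS of about 20 months, exponential survival and a correlation of 0.2 to 0.4 between quality of life and survival. All three are assumptions about this trial. The shift is zero with no link and larger if survival is shorter. The SD scale treats each item as roughly continuous, so the figures are approximate for 0-4 responses.

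The repeated-measures models do not remove the concern while their type and missing-data assumption are unstated. The consequence is limited to the interpretation of a secondary, exploratory objective; the primary analysis is untouched. This is a worthwhile improvement and not a flaw that threatens the trial.

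**What to change.** Amend the quality-of-life paragraph of Section 7.3.3:

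1. Alongside or in place of the raw means, show within-patient change from baseline, and profiles grouped by time of last assessment or death.
2. Give the number alive and the number completing FACT-G under each visit on every plot, and mark which items score higher as worse.
3. Specify the item models as random-effects cumulative logit models fitted by likelihood, and state the assumption: missingness may depend on observed quality of life.
4. Such a model implicitly extrapolates past death. It does not by itself give an estimate for patients while alive, so base the conclusion on the grouped profiles and word it as applying while alive.
5. Add one sensitivity analysis, by a pattern-mixture or joint model.
6. State whether FACT-G continues after removal under Section 8.1.1, so that this section and Section 6.2 can be read together.

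The cost is SAP wording and a little more analysis. Dates of death are already needed for OS, so items 1 to 5 call for no new data.

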#### *7.4. Early Stopping for Toxicity*

Toxicity will be monitored continuously, with protocol amendment being made as needed. For safety, we will consider that regimen to be excessively toxic and stop accrual if, at any time, the observed rate of grade 3-5 acute or late toxicity as defined above in Section 6.4.5  $\geq 33\%$  and at least 4 toxicities have been observed.

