### *1.3 Stereotactic body radiotherapy (SBRT)*

SBRT is technique that combines highly conformal radiotherapy with real-time imaging to deliver high doses of radiation in a small number of fractions. Modeled after intracranial stereotactic radiosurgery, SBRT has now been studied in a variety of extracranial locations including the spine, lung, liver, pancreas, and head and neck cancers. Because of the precise targeting, SBRT has the potential to improve upon the local control achieved with conventional EBRT while minimizing the dose to normal tissue. Most prospective randomized trials of conventionally fractionated EBRT for the treatment of locally-advanced pancreatic cancer have reported local control rates of 35%-55% (2-5). Koong, et al established the feasibility of using SBRT for locally-advanced pancreatic cancer in a phase I dose escalation study which achieved 100% local control with no treatment limiting toxicities at 25 Gy in a single fraction (10). A follow-up study combined conventionally fractionated 5-FU chemoradiotherapy with an SBRT boost resulting in 94% local control but no improvement in overall survival and an increase in toxicity compared to SBRT alone (11). A recent study combining full dose gemcitabine with single fraction SBRT reported 81% local control and 100% 1-year freedom from local progression. While acute toxicities were minimal, a significant number of subjects (47%) experienced Grade 2 or greater late toxicities, primarily duodenal ulcers (12). It is possible that these late toxicities may be reduced by increasing the degree of conformance of the radiation dose cloud and increasing the number of fractions, as studies comparing conventionally fractionated RT with hypofractionated RT have found an increased incidence of late GI toxicities in the hypofractionated group (13).

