#### *5.3 On-Treatment assessment and post-treatment toxicity evaluation*

All subjects will be seen prior to delivery of each fraction of SBRT with toxicity evaluated by physical examination. Subsequently, subjects will be evaluated for toxicity 10-12 weeks later and then every 3 months until at least 2 years. Toxicities will be scored by the NCI CTC AE version 4.0. Also see Section 6.0.

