#### *6.4.5 Safety evaluation*

All patients will be monitored for potential treatment-related toxicity throughout treatment as detailed in the schema. Toxicity will be graded according to the CTCAE, which is further detailed in section 8.2.1. Acute toxicity is defined as toxicity occurring within 3 months of completion of SBRT. Late toxicity is defined as toxicity occurring greater than 3 months after treatment.

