#### 7.2.2 Rate of Accrual

We anticipate that 2 to 4 study-eligible patients will be enrolled per month. Thus, our planned study size of 50 patients to be enrolled within 24 months is well within our capacity.

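### Section 7.4 gives its acute-or-late toxicity rate no denominator or minimum follow-up; taken over all treated patients, the rate is biased low during accrual

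*Combined protocol and SAP*

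**What the plan says.** Section 7.4 stops accrual if, "at any time, the observed rate of grade 3-5 acute or late toxicity" is 33% or more "and at least 4 toxicities have been observed". It also states: "Toxicity will be monitored continuously, with protocol amendment being made as needed". It names no denominator, minimum follow-up or adjustment for incomplete follow-up, and reports no operating characteristics.

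Section 6.4.5 sets the two windows: "Acute toxicity is defined as toxicity occurring within 3 months of completion of SBRT", and "Late toxicity is defined as toxicity occurring greater than 3 months after treatment". The late window has no stated upper limit. Under section 5.3, "subjects will be evaluated for toxicity 10-12 weeks later and then every 3 months until at least 2 years".

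On accrual, section 7.2.1 plans 24 months of entry and 24 months of further follow-up for 50 patients. Section 7.2.2 says: "We anticipate that 2 to 4 study-eligible patients will be enrolled per month".

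The only safety analysis set is in section 7.3.1: eligible patients who received at least one fraction. Section 7.4 does not refer to it.

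**The concern.** The rule pools two kinds of event with very different timing. Acute toxicity is known within 3 months. Late toxicity starts after 3 months and is followed for about two years, roughly as long as the whole accrual period. If every treated patient counts in the denominator from the first fraction, a patient treated last week counts as a completed non-event for late toxicity. The numerator lags and the denominator does not, so the rate is too low for as long as patients are entering.

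Section 7.4 states no other numerical safety limit. If the late rate really were above 33%, the rule could stay silent while much or all of the sample was treated. How likely that is depends on the denominator, the accrual speed and the onset pattern. The plan states only a range for the second and nothing for the other two.

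**Working it through.** **Plan's own figure.** The plan gives none for the stopping rule. Its one design figure, 94% power, reproduces: a simulated one-sample log-rank test with 50 patients, 2-year LPFS of 40% against 60%, 24 + 24 months and one-sided 0.05 gives 94.2%. The accrual inputs are therefore being read as intended.

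**Inputs from the documents.** 50 patients; entry over 24 months (50/24 = 2.08 a month) or at 4 a month (50/4 = 12.5 months); late window from 3 months; follow-up to 24 months; limits of 33% and four events.

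**Assumptions, not in the documents.** True late grade 3-5 risk of 40% or 50%, several onset patterns, even entry, and each toxicity known at onset.

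**Follow-up available during accrual.** With even entry over A months, the share past 3 months at the end of accrual is (A − 3)/A:
- A = 24: 21/24 = 87.5%.
- A = 12.5: 9.5/12.5 = 76%.
- Half are past 3 months when (A − 3)/A = 0.5, that is, at month 6.

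The share with 24 months completed is 0% at A = 24 or 12.5. At 2 a month (A = 25) it is (25 − 24)/25 = 4%. So most patients enter the late window during accrual, and almost none complete it.

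**Expected crude rate at the 50th enrolment.** Take a true late risk of 40% with onset uniform over 3-15 months. The visible share of events is the average over entry times of F(f), where F(f) = (f − 3)/12 between 3 and 15 months and 1 afterwards.
- A = 24: (6 + 9)/24 = 0.625, and 0.625 × 40% = 25%.
- A = 12.5: (9.5²/24)/12.5 = 0.301, and 0.301 × 40% = 12%.

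Both lie below 33% although the true rate exceeds it.

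**Chance of stopping before the 50th patient.** Simulation (6,000 to 20,000 trials per cell), late toxicity only, all enrolled patients as denominator, rule checked at each event. A range means that separate runs differed.

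| Late onset after SBRT | 40% risk, 2.08/month | 40% risk, 4/month | 50% risk, 2.08/month | 50% risk, 4/month |
|---|---|---|---|---|
| 3 months + exponential, mean 3 | 44% | 2% | 83-86% | 14-18% |
| Uniform 3-12 months | 26% | 0% | 67% | 0.4% |
| 3 months + exponential, mean 6 | 16% | 0.1% | 49% | 0.4% |
| Uniform 3-15 months | 14% | 0% | 47-49% | about 0% |
| Uniform 3-24 months | 0.2% | 0% | 3% | 0% |
| Seen at once (reference) | 96% | 96% | 99.9% | 99.9% |

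Acute events raise the pooled rate. Adding 10% acute toxicity to the 40% late case (uniform 3-15 months) gives about 57% at 2.08 a month and 2% at 4 a month.

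**Alternative estimators.** At a true 40% late rate (uniform 3-15 months), cumulative incidence raises stopping from 14% to about 93% at 2.08 a month, and from 0% to about 57% at 4 a month. False stops are as follows:

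| True toxicity | Crude | Cumulative incidence | Pooled, event-free patients weighted by follow-up/15 |
|---|---|---|---|
| 10% acute, no late | about 1% | 2-3% | 17-33% |
| 10% acute + 10% late | 0.5-2% | 21-28% | 37-45% |

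The weighted version fails because an early acute event counts as 1 while recently entered event-free patients count as almost 0. At 20% late toxicity alone, cumulative incidence stops falsely in up to about 31% of trials.

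**The case against.** Several stronger readings are tempting, and the documents do not support them.

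- A reader might infer that the plan divides by all patients treated so far. Section 7.4 says only that the rate is observed. The all-treated denominator is the natural reading given section 7.3.1, but it is not in the text.
- A reader might infer that most patients have not reached the late window. That is true only for about the first 6 months of accrual; the accurate statement is that they have not completed it.
- A reader might infer that the rule would almost never stop for late toxicity. That fits slow onset, or entry near 4 a month under most patterns. At the planned 24-month accrual with early onset it is wrong: at a true 50%, stopping reaches 83-86%.
- A reader might take section 1.3 on SBRT, where "a significant number of subjects (47%) experienced Grade 2 or greater late toxicities", as evidence that a high rate is expected. That figure is grade 2 or greater after single-fraction SBRT with gemcitabine; the rule concerns grade 3-5. Section 1.3.1 reports no acute or late grade 3-4 toxicity in 24 post-operative patients.

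There are also other safeguards. Section 7.4 allows amendment as needed, and section 8.1 provides monthly toxicity review with committee oversight. It would be unfair to call the 33% rule the only brake.

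All of this limits the claim without removing it. The review meetings carry no numerical criterion of their own, and the favourable series is small with a median follow-up of 1 year. A stopping rule exists for the case in which such a series misleads.

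**Conclusion.** The concern holds as a defect of specification with a known direction. Section 7.4 does not define its rate. On the only safety set the protocol defines, that rate understates late toxicity throughout accrual.

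The direction follows from the documents; the size does not. It rests on assumed onset times and on true late rates of 40-50%, which the documents neither give nor predict. Within those assumptions, detection at a true 50% varies from almost nil to 86%, depending on matters the plan leaves open. A safety rule with that spread is not adequately specified and should be changed. Since toxicity visits are 3 months apart, delayed detection could lower the crude figures further; the simulation does not include this.

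**What to change.** In section 7.4, keep the 33% and four-event limits and:

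1. Count patients with a grade 3-5 toxicity rather than toxicities, and name the set.
2. Compute the rate as a cumulative incidence estimate, censoring each patient at current follow-up, with death as a competing event.
3. Alternatively, apply the limits separately: to acute toxicity among patients with 3 months of follow-up, and to late toxicity on follow-up-adjusted data.
4. Do not use a pooled rate that weights event-free patients by the share of the window completed, because of the false stops shown above.
5. State the operating characteristics across a range of true rates, onset patterns and accrual speeds.

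The work is a paragraph of protocol text and a short monthly calculation from dates already collected. Section 7.3.3 already calls for onset relative to first treatment and for time-to-event methods. The real cost is more false stops at intermediate rates, as given above. The sponsor should weigh that openly when choosing between options 2 and 3. No estimator can count events that have not yet happened, so with slow onset and fast accrual detection will stay limited, and the stated operating characteristics should show this.

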#### *1.3.1 Experience with SBRT at the University of Pittsburgh Cancer Institute*

A retrospective review from our institution evaluated the outcome in 71 subjects with intact pancreatic cancer treated with SBRT (16). With a median follow-up of 12.7 months the freedom from local progression at 6 months and 1 year was 72% and 49%, respectively. Median overall survival for the entire group was 10.3 months. Treatment-related toxicity was minimal with only 3 patients experiencing acute grade 3 toxicity (4%). There was no recorded late toxicity. We have been treating patients with close or positive margins with SBRT as well. We recently examined outcomes in 24 patients treated post-operatively with SBRT (17). Sixty-six percent of the patients had positive margins and the remainder had close margins of 1-2.5mm. The median follow-up was 1 year. The freedom from local progression at 6 months and 1 year was 95% and 66%. There was no acute or late grade 3-4 toxicity, and two patients (8%) had late grade 1-2 toxicity, again demonstrating that when done properly, SBRT has a low potential for toxicity. The current study seeks to further investigate the impact of SBRT following resection with a close or positive margin. We hope to improve local control, and through the use of a shortened treatment schedule, allow patients to begin systemic therapy earlier.

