#### *5.4 Stereotactic Body Radiotherapy Risks*

Short-term side effects include but not limited to skin reaction, local hair loss, fatigue, abdominal pain, nausea, vomiting, diarrhea, increasing liver function abnormality, GI bleeding or perforation which may require surgical intervention. Long term side effects are less likely to occur but if they do occur are more likely to be permanent. They include local hair loss, liver function abnormality, diarrhea, small bowel obstruction which may require surgical intervention, spinal cord injury which could result in paralysis, and kidney function abnormality.

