## 8.0 DATA SAFETY AND MONITORING

### 8.1 Data safety monitoring plan

All subject data will be collected by the University of Pittsburgh Cancer Institute's Protocol Office. All data will be secured in a password protected file with observance of all applicable HIPAA regulation. A data safety monitoring board will meet monthly to evaluate toxicity for this trial. Subjects/adverse events will be discussed at these monthly disease center meetings. Unexpected serious adverse events will be reported to the IRB and DSMC, and minutes of the monthly disease center meetings will be reviewed at the DSMC meetings.

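### The accrual-stopping rule in 7.4 pools grade 5 with grades 3-4 and cannot act before four toxicities, so nothing in the plan requires a pause after one to three SBRT-related deaths

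*Combined protocol and SAP*

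**What the plan says.** Section 7.4 opens with a general commitment: "Toxicity will be monitored continuously, with protocol amendment being made as needed". It then gives the trigger: "we will consider that regimen to be excessively toxic and stop accrual if, at any time", two conditions hold together. The first is that "the observed rate of grade 3-5 acute or late toxicity as defined above in Section 6.4.5" reaches 33% or more. The second is a minimum count: "and at least 4 toxicities have been observed". Section 6.4.5, to which the rule refers, divides toxicity into acute and late at 3 months after SBRT. It does not separate fatal from non-fatal events.

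The other safety provisions are these:
- Section 8.1 has a board that meets monthly to evaluate toxicity, and the minutes of the monthly meetings go to the DSMC. Direct reporting is stated as follows: "Unexpected serious adverse events will be reported to the IRB and DSMC".
- Section 8.1.1 lists reasons for removing an individual subject, including related grade 4 toxicity.
- Section 8.2.1 asks for a telephone and a written report of serious events within 24 hours, to the Principal Investigator or the Clinical Research Office. The reporting criteria are on the IRB's website.
- Section 5.4 names among the known risks "GI bleeding or perforation which may require surgical intervention".

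**The concern.** A toxicity rule for a single-arm trial has to cope with two different signals: too many severe events overall, and a small number of fatal ones. The 7.4 rule addresses only the first. A death has the same weight as a grade 3 event, and the four-event floor makes the rule silent in the earliest patients, where least is known.

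The patients have had a resection, and the safety premise is favourable. Of the institution's 24 post-operative SBRT patients, section 1.3.1 reports: "There was no acute or late grade 3-4 toxicity". One related death would be hard to square with that premise. If no section says that enrolment waits while someone looks, the decision rests on case-by-case judgement, and at the 2 to 4 patients per month expected in 7.2.2, about that many more could enter between monthly meetings.

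**Working it through.** The plan gives no operating characteristics for the rule, so there is no stated figure to reproduce.

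**Inputs.** From 7.4: stop if x ≥ 4 and x/n ≥ 0.33, where x is the count of grade 3-5 toxicities and n the number of patients. From 4.1.1: N = 50. Assumptions, because 7.4 does not settle them: at most one counted toxicity per patient, each event known immediately, and the rule checked after every patient. The death rates below are illustrative; the documents give none.

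**Step 1, the boundary.** The smallest x that stops accrual at each n is:

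| Patients n | Toxicities needed |
|---|---|
| 1-3 | no stop possible |
| 4-12 | 4 (4/12 = 33.3%; 4/13 = 30.8% fails) |
| 13-15 | 5 |
| 19-21 | 7 |
| 28-30 | 10 |
| 49-50 | 17 |

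Three deaths in the first three patients give x/n = 100% but x = 3, so the count condition fails. With no other counted toxicity, x = 3 fails at every n. Yet the exact one-sided 95% lower limit for 3/3 is 0.05^(1/3) = 36.8%, already above the rule's own 33%.

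**Step 2, the probability of ever stopping.** Carry the distribution of x forward one patient at a time. From each unstopped x, move to x + 1 with probability p and stay at x with probability 1 − p. Remove any path that meets the rule and add its probability to the stopping total. Compare with the binomial chance of deaths in 50 patients, P(≥1) = 1 − (1 − p)^50 and P(≥3) = 1 − P(0) − P(1) − P(2). At p = 0.05 these are 1 − 0.0769 = 0.923 and 1 − (0.0769 + 0.2025 + 0.2611) = 0.4595.

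If deaths are the only grade 3-5 events:

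| True death rate p | Expected deaths (50p) | P(≥1 death) | P(≥3 deaths) | P(rule ever stops) |
|---|---|---|---|---|
| 5% | 2.5 | 92.3% | 46.0% | 0.24% |
| 10% | 5 | 99.5% | 88.8% | 3.0% |

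**Step 3, sensitivity to non-fatal toxicity.** The rule sees only the total grade 3-5 rate. The same recursion gives a stopping probability of 11.5% at a total rate of 15%, 27.6% at 20%, 49.3% at 25% and 82.1% at 33%.

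**Step 4, direction of the ascertainment assumption.** Immediate knowledge of events favours the rule. Late toxicity (6.4.5) arises more than 3 months after treatment, and at 2 to 4 patients per month, 3 × 2 = 6 to 3 × 4 = 12 more patients would enrol in that time.

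**Step 5, whether another section requires a pause.** Section 8.1.1 acts on the individual subject. Section 8.1 sets up review and reporting, and 8.2.1 sets up reporting; neither attaches a criterion for holding enrolment. The amendment clause in 7.4 is discretionary.

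**The case against.** The strongest reply is that a related death would not go unseen. The monthly board reviews toxicity without regard to expectedness, the 24-hour report in 8.2.1 is not confined to unexpected events, and 7.4 promises continuous monitoring. The investigator, the board, the DSMC or the IRB could each halt enrolment. This stands. It limits the point to the absence of a required pause, but a permitted response is not a prespecified one.

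Some stronger readings are tempting and are not supported:
- *The rule directs accrual to continue after deaths.* It does not. Section 7.4 says when accrual must stop; it does not forbid stopping sooner.
- *Any number of deaths is tolerated while the total stays under 33%, for example 16 of 50 (32%).* The rule applies at any time, not only at the end. Under the assumptions above, with 16 events in random order among 50 patients, an earlier look would already have stopped accrual in 91% of orderings.
- *A fatal bleed or perforation would be classed as expected and bypass the DSMC.* Section 5.4 lists these events but not death, and 8.2.1 does not define expectedness. A fatal event might be classed either way. What can be said is that the direct route in 8.1 depends on that classification.

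Two further objections stand in part. The rule counts toxicities without saying whether the unit is events or patients; if several events in one patient count, three patients could reach four. And the 0.24% and 3.0% figures describe deaths with no accompanying grade 3-4 toxicity, a pattern for which the documents give no evidence; a rule set at 33% is meant to stop rarely at such rates.

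**Conclusion.** The point holds as a gap in what the plan requires. Section 7.4 has no grade 5 trigger, and with one toxicity counted per patient, one to three related deaths without other counted grade 3-5 toxicity leave it unmet, at the start of the trial or later. No other section obliges anyone to hold enrolment.

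The three-of-three example rests on the counting unit, which the plan leaves open. The stopping probabilities rest on assumed death rates, immediate ascertainment and a look after every patient, and should be read as illustrations. The boundary itself is plain arithmetic on 7.4. A reader should not infer that the rule is useless: for pooled grade 3-5 toxicity it stops with probability 82% at a true rate of 33% and 96% at 40%. What it lacks is a response to a few deaths. This is worth correcting because the remedy is cheap and leaves the existing rule as it is.

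**What to change.** Keep the 33% and four-event rule. In 7.4:
- State that it counts patients with at least one qualifying toxicity, divided by patients treated.
- Add that any death judged at least possibly related to SBRT on the attribution scale in 8.2.1, expected or not, is sent to the DSMC at once, and that new enrolment is held until the DSMC has documented its review.

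In 8.1, add a cross-reference so that direct reporting of such a death does not depend on expectedness.

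The change is a few sentences. It needs no extra patients, visits or staff, since the DSMC already exists. Its downside is a possible short hold on accrual after a related death.
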